1. PURPOSE OF THE STUDY

a. Brief Summary

The current study seeks to evaluate an evidence-based family intervention for teens with type 1 diabetes and their parents to offset the psychosocial and diabetes self-management risks during this period. This study will collect survey and biomedical data to assess this program in a randomized controlled trial. 165 families (including an adolescent and parent) will be enrolled, complete surveys, provide biomedical data via glucose monitors and receive the intervention. The results of this study will inform future intervention redesign to provide more judicious interventions to be disseminated across diabetes care.

b. Objectives

This study will evaluate the relative efficacy of each of the individual intervention components and also identify the mechanisms of actions (mediators) that are most impacted by these types of interventions as well as most linked to long-term outcomes for adolescents. This information will provide a more in-depth understanding of family-based program efficacy for teens with adolescents and provide more judicious and streamlined intervention options to be offered in diabetes clinics in the future.

c. Rationale for Research in Humans

In order to optimize family-based interventions, we need to evaluate adolescent and parent outcomes.

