Glucose monitoring data will be collected via glucose monitors that are already in use, among participants already using these devices at the time of enrollment, with data being shared by the participant with the research team via secure online portals created and run by their corresponding device company. For participants who are not already using glucose monitors at the time of enrollment, Libre 2 glucose monitor devices will be provided by study staff, as well as training on use following FDA-approved self-start guides that are available online. Research staff will also provide support throughout use, and will be used to collect 2 weeks of data at each time point. A smaller set of surveys will also be conducted at approximately 2-, 4-, and 6-week follow-ups (after every 2 sessions for the intervention group and at corresponding time points for the control group). Participants will be asked to report their A1Cs (or gathered from medical records) at baseline and 6-month and 12-month follow-ups. If participants do not have an A1c result from the target period, they will be sent via mail a blood collection kit that can be completed at home and returned via mail to a laboratory where the specimen will be tested for HbA1c.

b. Procedure Risks

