Insul-In This Together Program: Optimizing Family-based Interventions for Adolescents With Type 1 Diabetes and Their Parents

Statistical Analysis Plan

NCT04589689

[figure not shown]
May 11, 2021

Statistical Analysis Plan

[figure not shown]
1. Planned sample size was 150 enrolled parent-adolescent dyads. The final sample included 157 parent-adolescent dyads.
2. Basic two-sided t-tests for primary and secondary outcomes using a p-value cutoff of <.05. Compared participants based on condition assignments: intervention versus waitlisted control.
3. Simple regression models: test main effects on outcomes at 3-month and 6-month follow-ups (in Mplus)
 - a. Covariates: Teen age, diabetes duration, baseline TIR, baseline QOL, and baseline outcome (if other than TIR or QOL)
 - b. Auxiliary variables (to inform data imputation, but not directly included in model): Teen gender, baseline A1c, Teen PAID, and Parent PAID
4. Moderation analyses: separate regression models for each outcome that include set of covariates and an interaction term of condition x moderator.
 - a. Covariates: age, diabetes duration, baseline QOL, and baseline TIR
 - b. Outcomes: QOL, TIR, A1c, Teen PAID, and Parent Paid
 - c. Moderators (at baseline):
 1. Closed loop
 2. A1c \leq 7.5%
 3. TIR \geq 70%
 4. Race/ethnicity
 5. Income
 6. Insurance
 7. Baseline level of corresponding outcome
5. Mediation analyses: single mediator models
 - a. Mediator: immediate posttest
 - b. Outcomes: 3-month and 6-month follow-ups
6. 12-month follow-up – combine both conditions and look through 6-months (but for control the 6-month value 12-month value)

Regression Model

6-Month Follow-Up

Moderation Models

Single Mediator Model

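### The written mediation item names no covariates, and neither covariate list elsewhere in the SAP holds the baseline mediator, so the mediator-to-outcome path may be confounded by baseline

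*SAP*

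**What the plan says.** The protocol makes mediation an objective. Section 1b says the study will "identify the mechanisms of actions (mediators) that are most impacted by these types of interventions" and also find which of them are most closely tied to long-term outcomes, so that leaner programs can be offered in clinics.

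SAP item 5 specifies the analysis in three phrases: "Mediation analyses: single mediator models", "Mediator: immediate posttest" and "Outcomes: 3-month and 6-month follow-ups". It does not name the mediator constructs, any covariates, or the test of the indirect effect.

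The two items before it do list covariates:
- Item 3a, main-effect regressions: "Covariates: Teen age, diabetes duration, baseline TIR, baseline QOL, and baseline outcome (if other than TIR or QOL".
- Item 4a, moderation models: "Covariates: age, diabetes duration, baseline QOL, and baseline TIR".

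Nothing says that either list carries over to item 5. The SAP closes with model labels, the last being Single Mediator Model. Its diagram is not visible in this copy.

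On timing, protocol section 2a says "A smaller set of surveys will also be conducted at approximately 2-, 4-, and 6-week follow-ups". It does not call any of these the immediate posttest or say which constructs they cover.

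**The concern.** Randomization protects the path from condition to mediator. It does not protect the path from mediator to outcome, because families are not randomized to their posttest mediator score. A family that starts with a better mediator score may also start with a better outcome, and both may persist. A model without baseline values counts that persistence as an effect of the mediator. If the program also shifts the mediator, multiplying the two paths gives an indirect effect even though changing the mediator does nothing to the outcome.

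The results are meant to guide which parts of the program are kept. A mechanism credited in error would misdirect that redesign.

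**Working it through.** The documents give no effect size, correlation or power figure for mediation, so there is no stated figure to reproduce. The check asks how large the bias could be.

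**Inputs from the documents.** 157 dyads (SAP item 1) and 1:1 allocation (protocol section 2a). Two-sided 0.05 comes from SAP item 2, "Basic two-sided t-tests for primary and secondary outcomes using a p-value cutoff of <.05". It is stated there for the t-tests and assumed here for the mediation paths.

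**Assumed inputs.** Stability s from baseline to follow-up, the same for mediator and outcome: 0.6, with 0.7 as a sensitivity value. Baseline mediator-outcome correlation ρ: 0.1 to 0.5. Program effect a on the mediator: 0.2 to 0.5 SD. True mediator-to-outcome effect: 0.

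**Step 1, size of the spurious path.** With standardized variables, mediator M1 = a·T + s·M0 + e and outcome Y1 = s·Y0 + u. Within arm, Cov(M1, Y1) = s²·ρ and Var(M1) = 1, so the unadjusted path is b = s²·ρ and the apparent indirect effect is a·s²·ρ.
- ρ = 0.1: 0.36 × 0.1 = 0.036
- ρ = 0.3: 0.36 × 0.3 = 0.108
- ρ = 0.5: 0.36 × 0.5 = 0.18, and with a = 0.5 the indirect effect is 0.5 × 0.18 = 0.09

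**Step 2, how often mediation is falsely declared.** Simulation by ordinary least squares, 2,500 to 3,000 replicates per setting, s = 0.6. Mediation is declared when both paths have p < .05.

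| ρ | No baseline covariates |
|---|---|
| 0.1 | 2.0% (a = 0.2) to 5.9% (a = 0.45) |
| 0.2 | 3.0% (a = 0.2) to 11.7% (a = 0.45) |
| 0.3 | 6.5% (a = 0.2), 11% to 13% (a = 0.3), 21.3% (a = 0.5) |
| 0.5 | 27.0% (a = 0.3), 55.7% (a = 0.5) |

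The mean simulated paths match s²·ρ.

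**Step 3, with baseline values.** With the baseline mediator and baseline outcome in both equations, the rate is about 2% to 6% and the mean path is about 0.

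**Step 4, sensitivity.**
- Stability 0.7, ρ of 0.3 and 0.5: 22.0% and 39.7% at a = 0.3; 39.7% and 77.6% at a = 0.5.
- Sobel test instead of joint significance, s = 0.6, ρ of 0.3 and 0.5: 3.3% and 10.4% at a = 0.3; 9.7% and 34.2% at a = 0.5.
- Program does not move the mediator (a = 0): at or below 4.6%.
- No baseline correlation (ρ = 0), a of 0.3 or 0.5: 2.0% to 5.2%.
- Baseline outcome alone as covariate, a of 0.3 or 0.5: 2.1% to 4.8%.
- All measures with reliability 0.8 (ρ = 0.5, s = 0.7): the baseline outcome alone leaves a path of about 0.04 and rates of 3.7% (a = 0.3) and 7.7% (a = 0.5). Both baselines leave 0.012 to 0.017 and 2.6% and 5.0%.

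**The case against.** The strongest reply is that the specification may lie in the diagram, which this copy does not show. That stands. A reader might infer that the trial will fit mediation models with no covariates, and the documents do not support this. They show only that the written item is silent.

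A second reply is that the item 3a set may be meant to apply throughout. If so, the baseline outcome is in the model, and that alone removes most of the bias, as step 4 shows. Baseline QOL and TIR are in both lists, so for those two outcomes either list would serve nearly as well. This also stands, but it is incomplete. Item 4a would not supply the baseline outcome for A1c or either PAID score, and no list supplies the baseline mediator, which still matters when measures are imperfectly reliable.

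A third reply is that the size depends on numbers the documents do not give. This is correct. A reader might take the upper figures as the expected error rate. They need a moderate baseline correlation together with a program effect of about half an SD. With a weak correlation and a small effect there is no inflation.

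Finally, baseline adjustment does not make the mediator-to-outcome path causal, because confounding can arise after baseline. That is true and limits what the fix achieves.

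**Conclusion.** The point holds as a gap in the written text with a conditional consequence. If item 5 is followed as it reads, the mediator-to-outcome path is confounded by baseline. A false indirect effect then needs three things: the program moves the mediator, mediator and outcome are correlated at baseline, and both are stable over time. Under the main assumptions (s = 0.6) the spurious path is 0.04 to 0.18 SD per SD and the false-mediation rate about 2% to 55%. Higher stability raises the rate and the Sobel test lowers it.

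A reader might also infer that the trial's main result is at risk. It is not: the primary 6-month comparison is between randomized groups and does not use the mediation models. What is affected is the stated objective of identifying mechanisms.

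**What to change.** In item 5, state the covariates in words: the baseline value of the outcome, the baseline value of the mediator, and the item 3a covariates, in both the mediator equation and the outcome equation. If the diagram already shows some of these, the text should say so.

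The sponsor should confirm which mediator constructs were measured at baseline. Baseline surveys and glucose data are collected (protocol section 2a), and baseline A1c and PAID appear among the auxiliary variables in item 3b, so baseline outcomes should be available. A baseline counterpart for each mediator is plausible but not documented. Where one is missing, adjust for the baseline outcome and say so.

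Add a sentence that the mediator-to-outcome path remains observational after adjustment. A sensitivity analysis for that path would be useful. A bootstrap interval for the indirect effect is optional and does not address this bias.

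The cost is a line or two of SAP text and a few lines of Mplus code, with no new data where the baseline measures exist. If unadjusted models have already been run, re-run them with the covariates and report both.
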